**Environmental Sampling:**

1. Sampling Frequency: Curtains were sampled on a weekly basis for the total duration of 3 weeks. So, every curtain was sampled three times during complete sampling duration. First 7 days was the time of exposure to contaminate leading with next 3 weeks of sampling.
2. Sampling Area: Each curtain was sampled for eight areas for the size of 50x50cm^2 each. Four areas from top side starting from patient’s head side to toe side on the bed, and four areas from bottom side moving from toe to head side. As the size of curtain varies from 430cm to 480cm in length, for the best results after pilot study, we calibrated 8 areas keeping 50 cm from above, 37cm from lateral margins and 57-70cm in between.

- Area 1: Upper Head side
- Area 2: Upper 2nd area
- Area 3: Upper 3rd area
- Area 4: Upper Toe Area

- Area 5: Lower Toe Side
- Area 6: Lower 2nd area
- Area 7: Lower 3rd area
- Area 8: Lower Head Area

[figure not shown]

Fig 3. Illustration of 8 sampling location on a curtain received from Rehabilitation ward of KH, Designated 50x50cm^2 area were sampled following the protocol

3. Sampling Side of the curtain: Sampling was done from the inner side of the curtain, (inner side was more exposed to the risk of contamination as a frequent touch of the patient on the bed, nursing staff, cleaning staff, monitoring staff, attendants, and doctor).
4. Sampling material: Polywipe sponge were used to sample 50x50cm^2 area on the curtain.
5. Sampling technique: Both sides of a sponge were used by swabbing on the curtain. Holding the sponge from the middle of one side with the right hand, keeping vertically, swab area starting from upper left margin towards the upper right margin of 50x50cm^2 area from one side of the sponge. The same method was used swabbing from right to left side with other side of the sponge. Sampling was done gently, slowly and softly by not repeating the swab to sampled area.
6. Sampling frame: 50x50cm^2 frame of plastic covered with a disposable plastic sheet was used as back support for smooth sampling and accurate measurement. Every time, sterilized plastic was removed and new sheet was used to reduce the chance of microbial spread or false positive result on control and treatment arm of the study

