## **Primary Outcome Measure:**

1. Change in total bacteria count and MRSA in control vs treatment patient privacy curtains

To quantify the effectiveness of antimicrobial coating, percentage change (both in log and linear scale) in mean bacterial count (CFU/m^2 units) in control versus treatment curtains is used. The data was collected in 3 phases of 4 weeks each, so the time frame used is representative of the complete observation period.

[Time Frame: 12 weeks]

2. Durability of antimicrobial coating in affecting bacterial load amongst treated patient privacy curtains

Change in bacterial load amongst treatment curtains is observed as a function of time during each phase of the data collection period (for 4 weeks). In total, data was collected in 3 phases of 4 weeks each, so the total observation period is 12 weeks and timeframe of each frame is 4 weeks.

3) [Time Frame: 12 weeks]

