**Protocol:**

**1. Curtain receiving, coating, coding, and transportation:**

1. Every 2nd week, HKUST team received 26 washed (routinely cleaned) curtains from rehabilitation ward linen room on ground floor.
2. 13 curtains were kept in a designated cabinet in the linen room at 3rd floor Rehabilitation ward 3B. These 13 curtains were coded according to assigned numbers as control curtains.
3. 13 remaining washed curtains out of 26 were transported to HKUST by using three large luggage bags
4. As each curtain absorbs approx. 3 Liters of the coating solution, so our team had ensured availability of 30 liters of C16 coating material on completion of each phase.
5. Our team preferably prepared fresh C6 coating and diluted C6 in tap water at the time of coating to prepare C16.
6. We had three 95 Liters capacity big containers, that were used to coat the curtains in HKUST premises during Pilot study.
7. The best practice to coat the curtain was dipping method (dip a dry curtain in a filled container of C16 coating).
8. Curtains were soaked/dipped for 30 minutes in coating material to absorb properly and uniformly.
9. After soaking, curtains were squeezed gently to remove extra solution/liquid and transferred to clean and dry container.
10. 13 wet coated curtains were transferred to laundry to dry as following:
  - a. Hot air of 65°C for 30 minutes.

- b. Cold air of 20°C for 3-5 minutes to reduce the temperature of curtains.
11. 13 dry, coated curtains were brought back to the linen room of rehabilitation ward, coding was done according to the assigned number to keep the study blind. Only principal investigator has the knowledge of the factitious codes to keep study double blind.
12. All the curtains (13 coated and 13 uncoated) were prepared for installation in 1 week including receiving, transportation, coating, drying, and coding during pilot study.
13. Drying protocol amendment
- Drying protocol was amended due to shedding of coating in heavy circular mechanical motion in laundry dryer. For this purpose, curtains were kept on room temperature for overnight, and next morning when there was no apparent dipping, they were shifted to walk in incubator of Pathology lab at 50°C for 24-36 hours for best drying results.
  - Drying in HKUST premises was difficult with minimum resources, heavy weight and humidity issue along with transportation.

\*1 extra pair of curtains for control and treatment end was kept as a back up

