## 2. Curtain installation:

1. Every 3rd week, our team changed the curtains from 2 cubicles (1 male and one female) according to curtain changing policy of hospital.
2. At the start of every phase of study, following the standard protocol; after taking official consent from ward manager we changed the curtains at once from both cubicles.
3. There were two types of curtains clippings, with metal ring and cloth strips so that curtains were changed according to the type of clips/ring.
4. As there was the capacity of 12 curtains in one cubicle, so six curtains were coated and six uncoated. The sequence was alternative as one coated next uncoated and so on. After installation, we informed ward manager about completion of curtain hanging in the designated ward and took first sample at day 7 because we gave sufficient time to curtains to be contaminate in hospital environment.
5. There was a backup pair of the curtain in case of need to change curtain due to spoilage, vomitus, blood or MDRO diagnosed the patient. Staff was informed to notify our team about the date and reason of curtain changing.

[figure not shown]

Fig 2. Illustration of curtains installation in cubicles as one control other treatment showing matched paired randomization

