## Post Sampling Procedures:

1. Arrangements of Agar Media Plates: Queen Elizabeth Hospital's (QEH) Media preparation unit prepared TSA and Chromagar MRSA agar plates according to needs of this research.
    - a. Principal investigator was notifying [name] (coordinator for media preparation on QEH) two weeks ago about the preparation of required media plates.
    - b. All the prepared media was preserved at 3-4°C in QEH. Media plates boxes were labelled as HKUST-TSA and HKUST-MRSA plates in different batches.
    - c. Prepared boxed were transferred to Kowloon Hospital's cold room for long term use as well as prevention from contamination.
    - d. For the media preparation, sampling team coordinated by emails or meet them in person if there was any change in requirement.
  2. Agar plates Standardization: As the agar plates were kept at lower temperature (3-4°C), agar plates should normalize to normal room temperature as recommended. We kept out the agar plates on the desk before going for sampling, and in the meanwhile, plates were ready to use after 3-4 hrs.
  3. Unboxing and labelling of agar plates: All the prepared plates were packed in boxes, so before using the plates, team was unboxing, calculating and separating two type of media plates. Each plate was labelled as
    - a. Code, i.e., 1040
    - b. Sampling area number (1-8)
    - c. Plate number (first or duplicate)
    - d. Location (Male/ Female)  
i.e. (M-1040-4-2)Male-code 1040- Area 4- sample 2
- 
4. Sample inoculation area: Samples were inoculated on the desks in Kowloon hospital pathology core lab. All the team members were participating in this procedure following safety measure, wearing PPE.
  5. Mixing of Sponges containing neutralizer bag: Before taking 100µl of a neutralizing solution, it was compulsory to mix sponge very well so that all suspected microbes would come out from the sponge into the solution. Mixing was gentle, continuous and for the period of a minimum 1 minute.
  6. Dilution in PBS: 100µl of neutralizing solution was diluted in 900µl of PBS, mixed well and then 100µl was put on agar plated to inoculate. This was performed for TSA plates because bacterial load was high and plates were unable to read.
  7. Inoculation Procedure:
    - a. 100µl of well mixed neutralizing solution was dropped by using 100 -200 µl pipette with sterilized pipette tube on Chromagar MRSA plates and spread homogenously

- by sterilized beads by gentle shaking

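### Durability is read from the trend in treated curtains, but the same areas appear to be re-wiped every week, so loss of effect cannot be separated from removal by earlier sampling

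*Combined protocol and SAP*

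**What the plan says.** **Sampling.** Under Environmental Sampling, item 1 sets weekly visits: "So, every curtain was sampled three times during complete sampling duration". Item 2 fixes where: "Each curtain was sampled for eight areas for the size of" 50x50 cm, four in an upper row and four in a lower row, each with a named position. The layout is given once: "we calibrated 8 areas keeping 50 cm from above, 37cm from lateral margins and 57-70cm in between". Item 5 has both faces of a sponge passed over each area. Post Sampling Procedures, item 3, labels each plate by curtain code, area number (1 to 8), plate number and male or female location. No section describes moving the areas between weeks or keeping some fabric unwiped for comparison.

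**Timing.** Curtain installation, item 4, says the team "took first sample at day 7 because we gave sufficient time to curtains to be contaminate in hospital environment". I take the three visits as days 7, 14 and 21 and call them weeks 1, 2 and 3.

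**Use of the time course.** Objective 1(i) is total bacterial count over time, within a comparison of coated and standard curtains. Primary outcome 2, durability, is narrower: "Change in bacterial load amongst treatment curtains is observed as a function of time during each phase". The Detailed Description plans ANOVA by phase and by week. Neither it nor the Data Analysis section allows for earlier wiping.

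**The concern.** A swab removes part of the load it measures. If the same spot is wiped again a week later, the second count is what the first wipe left behind plus about one week of new contamination. It is not the load after two weeks of undisturbed hanging.

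This matters most for primary outcome 2, because a trend within treated curtains has no control to absorb the effect. Removal flattens any build-up, so a coating that is losing its effect could look durable. Weeks 2 and 3 supply two thirds of all samples.

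**Working it through.** **1. The plan's own figures.** Curtains x 8 areas x 3 visits: 20 x 24 = 480, 24 x 24 = 576, 32 x 24 = 768, total 1,824 = 76 x 24. This matches the schedule table and the stated total. (The Detailed Description prints 786 for phase 3. That would sum to 1,842, so I use 768.) The sample size also reproduces. For a one-sided two-sample t-test with d = 0.20, alpha 0.05 and power 0.95, n = 542 per group, df 1,082, critical t 1.6463, noncentrality 0.20 x sqrt(542/2) = 3.2924 and power 0.9501.

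**2. Are the positions fixed?** For a row of four on a curtain of length L, the gap is (L - 2 x 37 - 4 x 50)/3. This is 52.0 cm at 430 cm and 68.7 cm at 480 cm. The stated spacing of 57-70 cm therefore varies about as much as curtain length would make it vary. It is not a sign of week-to-week shifting. With named positions, labels 1 to 8 and counts that fit eight areas at every visit, re-wiping is the natural inference. It remains an inference.

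**3. Effect on the trend.** The documents give neither r, the fraction removed by a swab, nor s, the fraction of unwiped load still present a week later. Both are assumptions, as is constant weekly deposition (1 unit).

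- Unwiped: U1 = 1, U2 = 1 + s, U3 = 1 + s + s²
- Wiped, with k = s(1 - r): W1 = 1, W2 = 1 + k, W3 = 1 + k + k²
- Bias in week t = log10(Wt/Ut)

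With full persistence (s = 1), the true rise from day 7 to day 21 is log10(3) = 0.48 log:

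| Removal r | Week 2 bias | Week 3 bias | Rise observed |
|---|---|---|---|
| 20% | log10(1.80/2) = -0.05 | log10(2.44/3) = -0.09 | log10(2.44) = 0.39 |
| 50% | log10(1.50/2) = -0.12 | log10(1.75/3) = -0.23 | log10(1.75) = 0.24 |
| 80% | log10(1.20/2) = -0.22 | log10(1.24/3) = -0.38 | log10(1.24) = 0.09 |

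With s = 0.5 and r = 50%, the week-3 bias is log10(1.3125/1.75) = -0.12. With s = 0 it is nil for any r.

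**4. Effect on the arm difference.** If s and r are the same in both arms, Wt/Ut is the same in both and cancels in the log difference, so there is no bias. If load persists on control fabric (s = 1) but not on coated fabric (s = 0), wiping lowers only the control count. The week-3 arm difference is then 0.09 to 0.38 log smaller than on unwiped fabric for r of 20% to 80%, and 0.43 log smaller for r of 90%.

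**5. What day 7 alone can carry.** 76 x 8 = 608 samples, 304 per arm. Noncentrality is 0.20 x sqrt(304/2) = 2.47. Power is 0.79 one-sided (0.69 two-sided), against 0.996 one-sided for 912 per arm. These figures follow the plan in treating samples as independent, so they ignore clustering within curtains. Weeks 2 and 3 hold 1,216 of 1,824 samples (67%).

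**The case against.** **Re-wiping is not stated.** The layout figure is missing from the text, and item 5 says: "Sampling was done gently, slowly and softly by not repeating the swab to sampled area". Read broadly, that could mean an area was never swabbed twice. But the sentence closes a description of the strokes of one swabbing and does not address later visits. The point stands as an inference that the sponsor can confirm or correct.

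**Both arms are wiped alike.** This is the strongest objection and largely holds. Objective 1(i) is comparative, and a failing coating should show as the arms converging, whatever the shared removal. Day 7 precedes any described wipe. A reader might infer that weeks 2 and 3 show only regrowth, and that neither count over time nor durability is measured. The documents do not support that. Growth on the fabric is not established, later counts still measure load under identical weekly wiping, and the arm contrast in each week stays informative. What the objection does not rescue is a durability outcome defined on treated curtains alone.

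**Full persistence is an extreme assumption**, least plausible for a coating described as contact-killing. That is fair, and it is why the range must start at nil. The planning effect of 0.20-0.21 log is also a between-arm difference. It gives a scale for the within-arm shifts in step 3, but those shifts do not by themselves threaten the arm comparison.

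**Stripping of the coating is not shown.** A reader might link swabbing to this note on coating preparation: "Drying protocol was amended due to shedding of coating in heavy circular mechanical motion in laundry dryer". That was heavy dryer motion, after which drying was changed. The swabbing is described as gentle. Loss of coating through swabbing is possible but has no evidence here.

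**Conclusion.** The point holds for primary outcome 2 as written. If the areas were re-wiped weekly, the trend within treated curtains cannot be separated from removal by earlier sampling. Under the stated assumptions the week-3 distortion runs from nil (no persistence) to 0.38 log at 80% removal with full persistence. At that upper end, a three-fold build-up would look almost flat.

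The control-treatment difference in each week is unbiased if removal and persistence are equal in both arms. That condition cannot be taken for granted, because a contact-killing, anti-adhesion coating is meant to change persistence and may change what a swab lifts. The weekly contrast is therefore the better measure of durability, with that limitation stated. The sample size arithmetic is not affected.

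**What to change.** The study is complete, so the remedy lies in analysis and reporting, and needs no new data:

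- State whether the eight positions were the same at all three visits.
- Define durability as the control-treatment difference by week (arm x week), in place of the trend in treated curtains alone.
- Report day 7 as the only undisturbed estimate, beside the full analysis and not instead of it.
- Describe weeks 2 and 3 as load under weekly wiping: residue plus about one week of new contamination.
- Limit durability claims accordingly, and say that wiping may act differently on coated fabric.

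The cost is a less direct durability statement and lower precision for the day-7 estimate (304 per arm, power about 0.79 one-sided on the plan's own basis).

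In a repeat study, balance fresh and previously wiped positions across visits, areas and arms. The computed gaps of 52-69 cm would take a 50 cm frame, though tightly on the shortest curtains. Moving most areas only at the last visit would not do. It would confound position with time, and the plan calls the eight areas highly touched without showing that the gaps between them are touched equally.

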### Sample size calculation using G-power 3.1.9.2

In our previous study carried out in orthopedics wards, a total of 2249 samples were taken from hospital surfaces over a study period of 1 year. The following was the mean and standard deviation of log total-bacteria-count in the previous study.

Group Statistics					
Type (1/2)		N	Mean	Std. Deviation	Std. Error Mean
log (CFU/m  )	treatment	1130	4.13126	.544325	.016193
	control	1119	4.32627	.531846	.015899

### Basic information of previous field study in orthopedic ward

#### Assumptions:

1. The sample taken may have a higher standard deviation than the previous study. SD assumed to be 1log.
2. 0.21 log reduction on the total bacteria count on the bed partition curtains was assumed. This was based on the difference of the control and the treatment group in the previous study.

t tests - Means: Difference between two independent means (two groups)

Analysis: A priori: Compute required sample size

Input: Tail(s) = One  
 Effect size d = 0.2000000  
 α err prob = 0.05

	Power (1- $\beta$ err prob)	=	0.95
	Allocation ratio N2/N1	=	1
Output:	Noncentrality parameter $\delta$	=	3.2924155
	Critical t	=	1.6462631
	Df	=	1082
	Sample size group 1	=	542
	Sample size group 2	=	542
	Total sample size	=	1084
	Actual power	=	0.9500669

Hence a minimum of 1084 specimens were adequate for our study. To best fit the wards size and sampling schedule, we reckon a sample size of 1800 was best suited for our study.

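### Coating is assigned to whole curtains (38 vs 38), but the sample size counts swabs and no coated-versus-control test names a curtain or pair term; if the tests are run on swabs, p-values can be too optimistic

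*Combined protocol and SAP*

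**What the plan says.** **Assignment.** Under Curtain receiving, coating, coding, and transportation, whole curtains are dipped. Under Curtain installation, six coated and six uncoated curtains hang in a cubicle: "The sequence was alternative as one coated next uncoated and so on". The Fig 2 caption reads "Illustration of curtains installation in cubicles as one control other treatment showing matched paired randomization".

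**Sampling.** Environmental Sampling gives eight areas per curtain and three weekly visits. Detailed Description item 5 gives 1824 samples from 76 curtains, 912 per arm.

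**Sample size.** The calculation is headed "t tests - Means: Difference between two independent means (two groups". Its inputs are d = 0.20, one-sided 5% and 95% power. It concludes "Hence a minimum of 1084 specimens were adequate for our study", and then "we reckon a sample size of 1800 was best suited for our study". It mentions no ICC, design effect or pairing.

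**Analysis.** Detailed Description item 7 and Data Analysis compare bacteria counts between arms by t-test and Mann-Whitney. Data Analysis adds chi-square and Fisher's exact tests for MRSA percentage and a rank-sum test for time to first MDRO contamination. ANOVA compares phases, weeks and wards, not curtains. Neither section names a mixed model, cluster adjustment or paired test, or states whether tests are one- or two-sided.

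**The concern.** Swabs from one curtain share its bed, its patient and its coating uptake, so they may be more alike than swabs from different curtains. A test that counts 912 vs 912 independent observations then uses too small a standard error. The tests at issue assess the first primary outcome at P < 0.05, so chance differences between curtains could pass as an effect of the coating.

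The direction depends on where the correlation lies. Curtain-specific correlation makes an unadjusted swab-level test too optimistic. Correlation shared by neighbouring coated and uncoated curtains cancels in the difference and makes it slightly conservative.

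**Working it through.** **1. Units.** The work plan lists 8 + 12, 12 + 12 and 16 + 16 curtains, that is 20, 24 and 32. Times 24 swabs this gives 480 + 576 + 768 = 1824. Curtains per arm: 912/24 = 38. With a 50% split, the possible pairs are 4 + 6 + 6 + 6 + 8 + 8 = 38. The figure 38 is derived, not printed.

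**2. The plan's own figure.** With d = 0.20, one-sided alpha 0.05 and 542 per group, the noncentrality is 0.20 x sqrt(542/2) = 3.2924, with 1082 df and power 0.9501. The 1084 reproduces, on the premise that every specimen is independent.

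**3. Which unit do the tests use?** Not stated. Three features point to swabs:
- the sample size is in specimens;
- the arms are reported as 912 vs 912;
- the only averaging described is over duplicate plates.

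The previous-study table behind the design does the same: 0.544325/sqrt(1130) = 0.016193, its printed standard error.

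**4. Error of a swab-level t-test.** Let r be the ICC (assumed; none is given) and f the curtain-specific share of it, the rest being shared by the neighbouring curtain of the other arm. The true variance of the arm difference is (2/38) x [f r + (1 - r)/24]. The naive variance is about 2/912. Their ratio is R = 1 + (24f - 1) r. True two-sided error is 2 x [1 - Phi(1.96/sqrt(R))]; one-sided it is 1 - Phi(1.645/sqrt(R)).

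| r | f = 1: R, two-sided / one-sided | f = 0.5: R, two-sided / one-sided | f = 0: R, two-sided / one-sided |
|---|---|---|---|
| 0.02 | 1.46, 10.5% / 8.7% | 1.22, 7.6% / 6.8% | 0.98, 4.8% / 4.8% |
| 0.05 | 2.15, 18.1% / 13.1% | 1.55, 11.5% / 9.3% | 0.95, 4.4% / 4.6% |
| 0.10 | 3.30, 28.1% / 18.3% | 2.10, 17.6% / 12.8% | 0.90, 3.9% / 4.2% |
| 0.20 | 5.60, 40.8% / 24.4% | 3.20, 27.3% / 17.9% | 0.80, 2.8% / 3.3% |

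Simulation agrees: two-sided 10.5/18.1/28.0/40.7% for f = 1 and 7.9/11.2/18.1/27.4% for f = 0.5; one-sided 8.5/12.7/18.4/24.5% and 6.7/9.4/12.7/18.2%. Mann-Whitney on swabs gave 15.8% and 29.5% at r = 0.05 and 0.10 (f = 1, two-sided, 1000 runs). A chi-square test of MRSA on 912 vs 912 swabs (f = 1, 5-40% positive assumed) gave about 10/18/28/41%.

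**5. Curtain-level alternatives (simulated, two-sided).** A paired test on curtain means holds 4.7-5.3% in every scenario. A two-sample test on curtain means gives 4.8-5.1% for f = 1 and 3.6/2.2/1.6/0.9% for f = 0.5, so it is valid but conservative.

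**6. Power with 38 pairs.** Noncentrality = 0.20/sqrt{(2/38) x [f r + (1 - r)/24]}, 37 df, SD 1. Example, r = 0.05 and f = 1: 0.20/sqrt(0.0526 x 0.0896) = 2.91.

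| r | f = 1: one-sided / two-sided | f = 0.5: one-sided |
|---|---|---|
| 0.02 | 96.6% / 93.1% | 98.4% |
| 0.05 | 88.8% / 81.0% | 95.7% |
| 0.10 | 74.6% / 62.9% | 89.4% |
| 0.20 | 55.0% / 42.0% | 75.8% |

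One-sided 95% power is kept up to r = 0.027 (f = 1) or 0.057 (f = 0.5). At the previous study's pooled SD of 0.538 and difference of 4.32627 - 4.13126 = 0.195, it is kept up to r = 0.188 (f = 1).

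**The case against.** The strongest reply is that the harm is conditional. It needs tests run on swabs, material correlation within curtains, and correlation not mostly shared by neighbours. No document settles any of these. One Data Analysis sentence describes the contamination level per item, which could mean one value per curtain, and a test on curtain means would be valid. This stands as a limit on the claim. A reader might infer that the trial's p-values are wrong; the documents show only that the plan permits this and that swabs are the likelier reading. If curtain means were intended, the unit is still unstated and 1084 is in the wrong unit.

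Variance between weeks or areas that is balanced across arms also works the other way. If it is 30% of swab variance (assumed), the two-sided errors become 7.0/14.8/25.9/39.4% (f = 1) and 4.1/8.0/14.4/24.8% (f = 0.5). The concern is reduced, not removed.

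A reader might also infer that the trial was underpowered. That is not shown: the plan raised the SD from about 0.54 to 1, and 1824 swabs exceed 1084 by a factor of 1.68.

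Finally, alternate hanging does not by itself define pairs, since an interior curtain has two neighbours of the other type. The work plan's 16 curtains per sex in phase 3 also conflicts with 12 curtains per cubicle and one cubicle per sex elsewhere. This stands, so a paired analysis cannot simply be assumed available.

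**Conclusion.** The concern holds, in conditional form. The plan assigns curtains and sizes the study on swabs taken as independent. It leaves the unit of analysis open and names no curtain or pair term in the coated-versus-control tests. If these are run on swabs, p-values for total count and MRSA percentage can be materially too small. The size rests on an assumed ICC and on how much of it neighbouring curtains share, and the possible range runs from no inflation to roughly eightfold (about 41% against 5%).

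Two further inferences are not supported. The mean difference, and so the reported percentage change, is not biased by clustering when swab counts are equal. Time to first MDRO contamination is untouched by swab clustering if it is one value per curtain, but Data Analysis does not say so explicitly; its rank-sum test also ignores the pairing.

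This must be fixed: it bears on the first primary outcome, and a method that holds its error rate at any ICC is available from the same data.

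**What to change.** - **Unit.** State the curtain as the unit of analysis. Average log10 CFU/m2 to one value per curtain and compare arms with a two-sample test on curtain means as the default. Use a paired test, or a mixed model with random curtain and pair effects, if the pairs in Fig 2 were fixed at installation and can be recovered.
- **Structure.** Reconcile the phase 3 curtain count with the stated cubicle capacity and allocation before using cubicle or pair terms. Allow for bed positions that recur across phases.
- **MRSA.** State whether the percentage is of swabs or of curtains. If of swabs, replace chi-square/Fisher with GEE or mixed logistic regression clustered on the curtain or pair.
- **Time to first MDRO.** State that it is one value per curtain.
- **Linkage.** The plan foresees replacements: "There was a backup pair of the curtain in case of need to change curtain due to spoilage", and "Staff was informed to notify our team about the date and reason of curtain changing". Use those records to assign each swab to the right curtain. Plate labels carry sex, code, area and plate number, but not week or pair. Link the code to the bed number on the bags and to the sampling date.
- **Sample size.** Say that 1084 holds only under independence. Give power for 38 vs 38 curtains over a stated ICC range, with one sidedness and one difference. The text says "0.21 log reduction on the total bacteria count on the bed partition curtains was assumed", the calculation uses 0.20, and the previous-study table gives 0.195. Report the observed ICC.

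Cost: SAP wording and re-analysis of existing data, with no new samples. P-values are likely to be larger and the stated power less favourable.

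### The 95% power claimed for 1084 specimens treats swabs as independent, but the coated unit is the curtain and each gives 24 swabs; at the plan's SD of 1 log, 76 curtains keep 95% one-sided only if the ICC is at most about 0.03

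*Combined protocol and SAP*

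**What the plan says.** The sample size section starts from a previous study on orthopaedic wards and tabulates its log counts: mean 4.13126 (SD 0.544325, n = 1130) on treatment and 4.32627 (SD 0.531846, n = 1119) on control. Two assumptions follow: "SD assumed to be 1log", and "0.21 log reduction on the total bacteria count on the bed partition curtains was assumed". The G-power output is labelled "t tests - Means: Difference between two independent means (two groups". Its inputs are one tail, d = 0.20, alpha 0.05, power 0.95 and 1:1 allocation. Its output is 542 per group, 1084 in total, with actual power 0.9500669. The text concludes "Hence a minimum of 1084 specimens were adequate for our study", then chooses 1800 to suit ward size and the sampling schedule.

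Other sections describe the unit that is treated and how often it is measured. Under curtain coating, item 7, the method is to "dip a dry curtain in a filled container of C16 coating", so a whole curtain receives the coating. Curtain installation, item 4, alternates coated and uncoated curtains within a cubicle. Environmental Sampling states "Each curtain was sampled for eight areas" and "So, every curtain was sampled three times during complete sampling duration". Detailed Description, item [5], reports 1824 samples from 76 curtains, 912 per arm. Data Analysis compares the arms by t test and Mann-Whitney test, and uses ANOVA for periods and wards. None of these sections gives an ICC, a design effect or a term for curtain.

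**The concern.** Swabs from one curtain share the same bedside, the same hands and, in the coated arm, the same soak and drying. Some positive correlation within a curtain is therefore to be expected, and 24 correlated swabs carry less information than 24 independent ones. The calculation counts them as 24 separate units.

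This is the only power statement in the document. A reader who accepts 95% for 1084 swabs, or more than that for 1824, may overrate the study's precision. How far depends on the ICC, which the documents do not give, and on the SD, which for curtains is assumed.

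**Working it through.** **1. Reproduce the plan's figure.** With n = 542 per group and d = 0.20, the noncentrality is 0.20 × √(542/2) = 3.2924. The critical t on 1082 df, one-sided, is 1.6463. The noncentral t then gives power 0.95007, which matches the document. The arithmetic is sound; the independence assumption is what is in question.

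**2. Cluster size.** 8 areas × 3 visits = 24 swabs per curtain. This agrees with 1824/76 = 24 and with the phase counts in the work plan: 480/20, 576/24 and 768/32 are each 24. The minimum of 1084 swabs is 1084/24 = 45.2, about 46 curtains (23 v 23). The 1824 swabs are 38 v 38 curtains.

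**3. Formula with the curtain as the unit.** With an exchangeable ICC,
- variance of a curtain mean: V = SD² × (ICC + (1 − ICC)/24)
- noncentrality for k curtains per arm: difference / √(2V/k)
- df = 2k − 2: 74 for 38 v 38, 44 for 23 v 23.

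Example at SD 1, ICC 0.10 and k = 38: V = 0.10 + 0.90/24 = 0.1375. The standard error is √(2 × 0.1375/38) = 0.0851 and the noncentrality is 0.20/0.0851 = 2.351. Against a critical t of 1.666, one-sided power is 75%.

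**4. Results.** The ICCs 0.05, 0.10 and 0.20 are assumptions. The previous-study rows use its own figures. The pooled SD is √((1129 × 0.544325² + 1118 × 0.531846²)/2247) = 0.538, and the difference is 4.32627 − 4.13126 = 0.195.

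| Scenario | Sides | ICC 0.05 | ICC 0.10 | ICC 0.20 | Largest ICC keeping 95% |
|---|---|---|---|---|---|
| SD 1, diff 0.20, 38 v 38 | one | 89% | 75% | 56% | 0.028 |
| SD 1, diff 0.20, 38 v 38 | two | 82% | 64% | 43% | 0.016 |
| SD 1, diff 0.20, 23 v 23 | one | 72% | 56% | 40% | none |
| SD 0.538, diff 0.195, 38 v 38 | one | >99.9% | 99.5% | 94.5% | 0.19 |
| SD 0.538, diff 0.195, 38 v 38 | two | 99.9% | 98.8% | 89.8% | 0.15 |

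For 23 v 23 curtains at SD 0.538 and difference 0.195, 95% holds up to an ICC of 0.098 one-sided or 0.072 two-sided.

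Cross-check of the first limit by design effect, 1 + 23 × ICC: 1824/1084 = 1.683, so ICC = 0.683/23 = 0.030. The slightly lower 0.028 comes from using 74 df.

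**5. Effect of the layout.** Coated and uncoated curtains alternate, so variation shared by both arms could be removed by an analysis that adjusts for blocks. Assume that half of the between-curtain variance lies between the six sex-by-phase groups. Then V = SD² × (0.5 × ICC + (1 − ICC)/24) on 69 df. At SD 1, power for 38 v 38 is 96% / 90% / 76% one-sided and 92% / 83% / 65% two-sided. 95% holds up to an ICC of 0.059 one-sided or 0.033 two-sided.

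**6. Two minor inconsistencies.** The table gives a difference of 0.195, the text says 0.21 and the run uses 0.20. The run is one-tailed, while the analysis sections give only P < 0.05 with no side. Neither is decisive alone: 912 v 912 independent swabs at SD 1 give 98.6% two-sided power at 0.195 and 99.0% at 0.20.

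**The case against.** The limit of about 0.03 belongs to one scenario: SD 1 log, one-sided, no use of blocking. The plan presents the SD of 1 log as a cautious inflation, and the only observed SD is about 0.54. At that SD and a difference of 0.195, 76 curtains tolerate an ICC near 0.19. With the same assumed half-between-blocks split as well, 95% would hold to about 0.40 one-sided or 0.32 two-sided. The plan claims 95% for 1084 specimens, not for 76 curtains, and the larger number actually collected absorbs a design effect of 1.68. Data collection is complete, so restating planning power changes no estimate or p-value.

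Much of this is fair and limits the size of the point. The favourable cases are real possibilities. However, the observed SD comes from hospital surfaces on orthopaedic wards, not from these curtains, and the plan itself chose 1 log because the new samples might vary more. The Fig 2 caption mentions matched pairs, but Data Analysis specifies no paired or blocked comparison of the arms. The increase to 1800 is justified by ward size and schedule, not by clustering. None of this rescues the claim for 1084: on the plan's own inputs it has no margin, so any positive ICC takes it below 95%.

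**Conclusion.** The concern holds. The 95% figure for 1084 specimens rests on an independence assumption that the sampling scheme does not support. At the plan's SD of 1 log and a difference of 0.20, an ICC of 0.10 would leave about 56% one-sided power for the 1084 minimum and 75% for the 76 curtains sampled. At the previous study's SD and difference, the 76 curtains would still have 99.5%.

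These figures rest on assumed ICCs, exchangeable correlation within a curtain, equal cluster sizes of 24 and, except in step 5, an unblocked comparison of curtain means. They do not show that the study was underpowered. They show that the stated power is unsupported and that its true value could lie anywhere in a wide range.

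**What to change.** Withdraw the statement that 1084 specimens are adequate for 95% power. Restate power with the curtain as the unit (38 v 38, 24 swabs each), over a range of ICCs and for both SDs (1 log and 0.538).

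Inform the ICC from the pilot or survey swabs where their sampling scheme allows; the eight areas were calibrated after the pilot, so earlier swabs may follow a different layout. Otherwise use the 912 control swabs (38 curtains × 24), for variance components only and labelled as done after the fact.

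Note that alternating curtains within cubicles may recover some precision if the analysis uses it. Use one effect value throughout, state the same number of sides in the calculation and the analysis, and give two-sided power as well.

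The cost is one rewritten section and one variance-components estimate on data already held. No more curtains are needed. The drawback is that the stated power becomes less favourable and is a range, not a single figure.
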